5.5.1.3. Normalization of CRP and ESR

The normalization of CRP is defined as CRP<10 mg/L or <1 mg/dL and the normalization of ESR is defined as ESR<30 mm/hr.

5.5.1.4. Patient's Global Assessment of Disease Activity (PGA)

The patient's global assessment of their GCA disease activity is recorded on a 10-cm VAS with verbal anchors on how their GCA feels today are “very poor” on the far-left side of the scale and “very well” on the far right of the scale. For this endpoint, a positive change from baseline reflects an improvement, and a negative change from baseline reflects a worsening.

The baseline measurement for the PGA is defined as the closest measurement taken prior to the initiation of the Week 0 administration.

5.5.1.5. Pain Severity Assessment

Participants will be asked to rate the severity of their average pain now on 10-cm VAS with anchors ranging from 0, “no pain” to 10, “worst pain imaginable”. For this endpoint, a negative change from baseline reflects an improvement, and a positive change from baseline reflects a worsening.

The baseline measurement for the pain assessment is defined as the closest measurement taken prior to the initiation of the Week 0 administration.

5.5.1.6. SF-36

The Medical Outcome Study health measure entitled the 36-item Short-Form Version 2 acute (SF-36v2 acute) health survey questionnaire was developed as part of the Rand Health Insurance Experiment and consists of 8 multi-item scales.

- Limitations in physical functioning due to health problems.
- Limitations in usual role activities due to physical health problems.
- Bodily pain.
- General mental health (psychological distress and well-being).
- Limitations in usual role activities due to personal or emotional problems.
- Limitations in social functioning due to physical or mental health problems.
- Vitality (energy and fatigue).
- General health perception.

These scales will be scored following two approaches: Based on transformed raw scores that range from 0 to 100 with higher scores indicating better health, and standardized scores using a *T*-score transformation to compare to the US general population normative values (mean=50, SD=10) or other populations of interest.

Another algorithm yields 2 summary scores, the Physical Component Score (PCS) and Mental Component Score (MCS). These summary scores are also scaled with higher scores indicating better health. The concepts measured by the SF-36 are not specific to any age, disease, or intervention group, allowing comparison of relative burden of different diseases and the relative benefit of different treatments).

Change from baseline in SF-36 score measures the change in health-related quality of life, where a positive change indicates an improvement, and a negative change indicates a worsening.

Missing data will be handled following the Full Missing Score Estimation (Full MSE) method, which assumes that the missing item responses in a given scale are the same as the response to the scale's answered item. The final item response values are assigned accordingly. This approach should not be used in the Physical Functioning (PF) domain scale, but the PF can be estimated using item response theory (IRT), which is performed by the QualityMetric Health Outcomes™ Scoring Software 5.0.

5.5.1.7. FACIT-fatigue

The FACIT-fatigue version 4.0 is a 13-item questionnaire formatted for self-administration that assesses patient-reported fatigue and its impact upon daily activities and function over the past 7 days. Participants will be asked to answer each question using a 5-point Likert-type scale (0=Not at all; 1=A little bit; 2=Somewhat; 3=Quite a bit; and 4=Very much). Questions 1-6 and 9-13 are scored in reverse order. If 7 or more questions are answered, then the score can be calculated and is adjusted by the number of available questions. The interpretation of FACIT-fatigue scores is such that a higher score indicates less fatigue, with a range of possible scores of 0-52, with 0 being the worst possible score and 52 the best.

Change from baseline in FACIT-fatigue scores measures the change in fatigue where a positive change indicates an improvement, and a negative change indicates a worsening.

Missing data will be handled by calculating a total score that is prorated from the score of the answered items as long as more than 50% of the items (i.e., at least 7 of 13) were answered.

5.5.1.8. Physician's Global Assessment of Disease Activity (PhGA)

The physician's global assessment independent of participants' assessment of the patients GCA activity is recorded on a 10-cm visual analog scale (VAS) with verbal anchors "No GCA" on the far-left side of the scale and "Very severe GCA" on the far right of the scale. For this endpoint, a negative change from baseline reflects an improvement, and a positive change from baseline reflects a worsening.

The baseline measurement for the PhGA is defined as the closest measurement taken prior to the initiation of the Week 0 administration.

5.5.1.9. Analysis Methods

Unless otherwise specified, the analysis population will be the FAS defined in Section 4. The endpoints will be summarized by intervention group as specified in Section 5.6.

Analyses for binary endpoints (proportion of responders) over time will be the same as the analyses for the above secondary endpoints 1-4 in Table 2 based upon the primary estimand only.

Unless otherwise specified, the analyses for continuous endpoints at Week 28 and Week 52 will be based on the following strategies to handle ICEs and missing data:

- ICEs in categories 1-3 in the primary estimand (definitions in Section 5.3.2) will be handled with the Composite Strategy. Participants experiencing ICEs 1-3 will have a zero change (or zero improvement) from baseline assigned from that point onward.
- ICE in category 4 in the primary estimand will be handled by the Treatment Policy strategy. The analysis will be performed using observed data regardless of intercurrent events. For participants experiencing multiple ICEs, an ICE in categories 2 or 3 of the primary estimand will override an ICE in category 4.
- Missing data will not be imputed after applying the rules for intercurrent events.

Simple descriptive statistics, such as n, mean, SD, median, IQ range, minimum and maximum for these continuous variables.

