5.3.2.1. Primary Estimand

The primary estimand, based on the above primary objective, is defined by the following 5 components which assess the treatment effects not only based on the variable measurements, but also based on intercurrent events:

- **Study intervention:**
 - Guselkumab in addition to 26-week GC-taper (including participants who received 400 mg IV induction doses followed by 200 mg SC dosing from Week 12 onwards and participants that received 200 mg SC dosing only)
 - Placebo in addition to 26-week GC-taper
- **Population:** adult participants 50 years or older with active new-onset or relapsing GCA (defined by American College of Rheumatology criteria).
- **Variable:** Binary response variable, where a responder is defined as a participant achieving GC-free remission at Week 28. A participant with an intercurrent event in categories 1-3 defined below will be considered as a non-responder.
- **Summary Measure (Population-level summary):** difference in the proportions of GC-free remission at Week 28 between the guselkumab group and the placebo group.
- **Intercurrent Events:**

Intercurrent Events (ICEs)	Strategy for Addressing Intercurrent Events and Its Description
1. Discontinuation (DC) of study intervention due to lack of efficacy or an AE of worsening of GCA. 2. Initiation of a protocol-prohibited medication during the study that could improve GCA. 3. Initiation of GC rescue therapy.	Composite Strategy: A participant with this intercurrent event is considered as a non-responder after this event. The occurrence of this intercurrent event is captured in the variable definition.
4. Discontinuation of study intervention other than ICEs #1	Treatment Policy: Use observed data regardless of whether or not this intercurrent event had occurred

Note: For participants experiencing multiple ICEs, an ICE in categories 2 or 3 will override an ICE in category 4.

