5.4.1.2. Estimands

The study intervention and population are the same as the primary estimand. The following table provides the list of variables, summary measure (population-level summary) and intercurrent event for secondary endpoints.

Table 2: List of Secondary Endpoints and Estimands

Estimands	Variable	Summary Measure (Population-level summary)	Intercurrent Events
Sec 1	Binary response variable, where a responder is defined as a participant achieving GC-free remission from Week 28 through Week 52 by visit	Difference in the proportions of achieving GC-free remission between the guselkumab groups and the placebo group	Using the same analysis strategies as the primary estimand.
Sec 2	Binary responder variable, where a responder is defined as a participant achieving GC-free remission and normalization of ESR at Week 28 and from Week 28 through Week 52 by visit	Difference in the proportions of achieving GC-free remission and normalization of ESR between the guselkumab group and the placebo group	
 The analysis strategies for the Week 28 endpoint will be the same as those for the primary estimand. The analysis strategies for summary over time by visit from Week 28 through Week 52 are the same as those in #1 in this table.

Estimands	Variable	Summary Measure (Population-level summary)	Intercurrent Events
Sec 3	Binary response variable, where a responder is defined as a participant achieving GC-free remission and normalization of CRP at Week 28 and from Week 28 through Week 52 by visit	Difference in the proportions of achieving GC-free remission and normalization of CRP between the guselkumab group and the placebo group	
 1. The analysis strategies for the Week 28 endpoint will be the same as those for the primary estimand. 2. The analysis strategies for summary over time are the same as those in #1 in this table.

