5.4.1.3.1. Binary Endpoints (Secondary Endpoints 1 - 4)

Analyses for binary secondary endpoints (proportion of responders) at Week 28 will be the same as the primary endpoint.

For secondary binary endpoints at Week 28, Cochran-Mantel-Haenszel chi-square statistic stratified by baseline disease status (new-onset and relapsing GCA), and the baseline GC dose (≤ 30 mg/day or > 30 mg/day) at a 2-sided significance level of 0.10 will be used to compare between the guselkumab and the placebo groups. Difference in response rates between the 2 intervention groups at Week 28 adjusted for baseline disease status (new-onset and relapsing GCA), and the baseline GC dose (≤ 30 mg/day or > 30 mg/day) using Mantel-Haenszel weight and the corresponding 90% CI will be presented.

For the summary over time by visit, after accounting for the ICEs for the primary estimand, any missing data for an endpoint will be imputed as not achieving the associated binary endpoints at Week X.

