5.5. Exploratory Endpoints Analysis for the Main Study

Objective: To evaluate the efficacy of guselkumab with a compared to placebo, in combination with a 26-week GC taper regimen, in adult participants with new-onset or relapsing GCA for the following exploratory endpoints:

Other Efficacy Endpoints

- Summary of signs, symptoms, and elevated CRP and/or ESR due to GCA disease flares
- Proportion of participants who experience at least one GCA disease flare or discontinuation of study intervention due to AE of worsening of GCA through week 28 and from Week 28 through Week 52 by visit
- Proportion of participants in sustained remission through Week 52 following remission at Week 8
- Proportion of participants in sustained remission through Week 52 following remission at Week 12
- Proportion of participants in sustained remission through Week 52 following remission at Week 16
- Proportion of participants in sustained remission from Week 28 through Week 52 by visit following remission at Week 8
- Proportion of participants in sustained remission from Week 28 through Week 52 by visit following remission at Week 12
- Proportion of participants in sustained remission from Week 28 through Week 52 by visit following remission at Week 16
- Cumulative GC dose through Week 28 and through Week 52 by baseline disease status (new-onset or relapsing GCA)
- Cumulative GC dose through Week 28 and through Week 52 by baseline GC dose (≤ 30 mg/day or > 30 mg/day)
- Change from baseline in ESR through Week 28 and from Week 28 through Week 52 by visit
- Proportion of participants with normalization of ESR through Week 28 and from Week 28 through Week 52 by visit
- Change from baseline in CRP through Week 28 and from Week 28 through Week 52 by visit
- Proportion of participants with normalization of CRP through Week 28 and from Week 28 through Week 52 by visit

Sustained remission through Week 52 is defined as: No signs and symptoms of GCA through Week 52, and completion of the protocol defined GC taper, and not having required GC rescue therapy at any time by Week 52.

Efficacy data through Week 28 and through Week 52 will be summarized and displayed by the following intervention groups:

1. Placebo
2. Guselkumab

Clinical Outcome Assessments (COAs)

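### The exploratory flare-proportion endpoint inherits a responder rule: participants lost without an event count as flare-free, and the coding of intercurrent events is left undefined

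*SAP*

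**What the plan says.** The endpoint is in SAP Section 5.5: "Proportion of participants who experience at least one GCA disease flare or discontinuation of study intervention due to AE of worsening of GCA". It is assessed up to Week 28 and then by visit to Week 52. Section 5.5.1, which holds the endpoint definitions, has no entry for it.

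The method comes through a chain of cross-references:

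- Section 5.5.1.9 is the only methods text for main-study exploratory binary endpoints: "Analyses for binary endpoints (proportion of responders) over time will be the same as the analyses for the above secondary endpoints 1-4". It points to Table 2 and limits the analysis to the primary estimand.
- Table 2 (Section 5.4.1.2) gives, for secondary endpoint 1, "Using the same analysis strategies as the primary estimand".
- The primary estimand (Section 5.3.2.1) lists intercurrent event (ICE) 1, "Discontinuation (DC) of study intervention due to lack of efficacy or an AE of worsening of GCA"; ICE 2, starting a prohibited medication that could improve GCA; and ICE 3, "Initiation of GC rescue therapy". All three follow the composite strategy: "A participant with this intercurrent event is considered as a non-responder after this event".
- For by-visit summaries, Section 5.4.1.3.1 adds that "any missing data for an endpoint will be imputed as not achieving the associated binary endpoints at Week X".

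In the same Table 2, time to first flare or discontinuation for worsening (secondary endpoint 6) and the number of such events (secondary endpoint 7) are handled by treatment policy.

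**The concern.** The rules for secondary endpoints 1-4 were written for outcomes that are good to achieve. Coding a participant with an intercurrent event or missing data as not achieving remission is the cautious choice. The flare proportion runs the other way: achieving it means having the bad outcome. The same words then no longer give a cautious result, and for the intercurrent events they no longer give a defined one.

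At stake is whether two programmers would produce the same table, whether participants lost to follow-up are silently counted as treatment successes, and whether the flare proportion would agree with the Kaplan-Meier curve drawn from the same events.

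**Working it through.** **1. The plan's own figure.** The documents give no figure for the flare proportion. The arm sizes, 17 placebo and 34 guselkumab, come from SAP Section 3. They can be checked against the stated 82% power for 40% versus 80% at two-sided alpha 0.10 (pooled Z test with continuity correction):

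- pooled proportion = (17 × 0.40 + 34 × 0.80)/51 = 0.667
- null SE = √(0.667 × 0.333 × (1/17 + 1/34)) = 0.140; alternative SE = √(0.24/17 + 0.16/34) = 0.137
- correction = 0.5 × (1/17 + 1/34) = 0.044
- power = Φ((0.40 − 0.044 − 1.645 × 0.140)/0.137) = 0.820

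The 82% reproduces. Nothing below changes it.

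**2. Missing data.** The by-visit rule imputes not achieving the endpoint. The endpoint is having at least one event, so the imputed value is no event. This step does not depend on what responder means. It applies only to participants lost without a prior event, because someone who flared and then left already has an observed outcome. The gap between coding one such person as flare-free and as an event is:

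- guselkumab: 1/34 = 2.9 percentage points
- placebo: 1/17 = 5.9 percentage points

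The documents state no dropout rate. For one to three such losses per arm, the gap is 2.9 to 8.8 points (3/34) in guselkumab and 5.9 to 17.6 points (3/17) in placebo. At Week 28 itself, Section 5.3.3 uses non-responder for missing data, so that time point also carries the ambiguity in step 3.

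**3. Intercurrent events.** Section 5.3.2.1 describes the primary variable as "Binary response variable, where a responder is defined as a participant achieving GC-free remission at Week 28", so a responder is someone who achieves the endpoint. For the flare proportion, non-responder can be read in two ways:

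| Situation | Endpoint as named | Non-responder = does not achieve the endpoint | Non-responder = bad outcome |
|---|---|---|---|
| Stopped for an adverse event of worsening GCA (ICE 1) | event | no event | event |
| Stopped for lack of efficacy only, no flare (ICE 1) | no event | no event | event |
| Prohibited medication, no flare (ICE 2) | no event | no event | event |
| Rescue GC after a flare (ICE 3) | event | no event | event |
| Rescue GC without a flare (ICE 3) | no event | no event | event |

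Neither reading matches the endpoint as named. The first goes wrong where it matters most. Stopping for worsening GCA is itself part of the endpoint, and a flare, by the definition in SAP Section 5.3.1, needs a GC increase and so usually brings rescue. The second creates flares that did not happen. SAP Appendix 8 counts any oral GC for a non-GCA indication and any intra-articular GC as prohibited medication, and Protocol Section 6.8.1 allows rescue GC for adrenal insufficiency.

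**4. Consistency.** Secondary endpoints 6 and 7 use the same two components and keep events as observed, whatever intercurrent events occur. Either column on the right of the table would give a proportion that can disagree with those analyses.

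**The case against.** The SAP never says that rescue or discontinuation is coded as no flare; it says non-responder. The bracketed words in the Section 5.5.1.9 sentence could mean that a flare proportion, which is not a responder proportion, falls outside the rule. The composite strategy treats the intercurrent event as captured in the variable definition, and discontinuation for worsening is already named in this endpoint. Non-responder status also applies only after the event, and the endpoint is cumulative, so a recorded flare need not be undone by the rescue that follows. Participants who stop treatment may stay in follow-up, and ICE 4 uses observed data. The missing-data rule sits under a heading confined to secondary endpoints 1-4.

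Most of this stands, and it limits the point. A reader might infer that the rule erases the flares and drives both arms to about 0%. The documents do not support that. It would require recorded events to be overwritten, which no text states, and event rates that the documents do not give. As an illustration, assume true proportions of 60% placebo and 20% guselkumab. These are the complements of the assumed remission rates and an upper bound, since non-remission also includes stable active disease, taper non-adherence and missing data. Let a share s of events be overwritten, so that the reported proportion = true proportion × (1 − s). Then s = 1 gives 0% versus 0%, s = 0.75 gives 15% versus 5%, and s = 0.5 gives 30% versus 10%. With 40% and 15% assumed instead, s = 0.5 gives 20% versus 7.5%. The 0% result is the extreme of one reading.

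Two parts of the objection do not stand. The heading of Section 5.4.1.3.1 gives no protection, because Section 5.5.1.9 imports its rules by reference. And if the bracket does exclude this endpoint, the endpoint has no rule for intercurrent events or missing data at all.

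**Conclusion.** The point holds in a limited form. A responder rule is applied to an unfavourable endpoint with no exception. Its by-visit missing-data wording, taken literally, counts participants lost without a prior event as flare-free, at 2.9 points each in guselkumab and 5.9 in placebo. The meaning of non-responder after ICEs 1-3 is undefined for this endpoint, and neither available meaning gives the endpoint as named.

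The per-person figures rest only on the planned arm sizes of 34 and 17; the total effect depends on the number of such losses, which is not known. It would go too far to say that every dropout counts as flare-free, or that the plan codes the events themselves as non-events. The endpoint is exploratory, and the same events are analysed under treatment policy in secondary endpoints 6 and 7. No conclusion from the primary analysis, the power calculation or the secondary endpoints changes.

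**What to change.** Add a short definition to SAP Section 5.5.1 and exempt this endpoint from the binary rule in Section 5.5.1.9:

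- Count as events only observed flares meeting the Section 5.3.1 definition and discontinuations of study treatment for an adverse event of worsening GCA, whatever intercurrent events occur, as for secondary endpoints 6 and 7.
- Do not count ICEs 1 and 3 wholesale. ICE 1 includes discontinuation for lack of efficacy without such an adverse event, and rescue GC can be given for adrenal insufficiency. Prohibited medication alone is not an event.
- For participants lost without an event, do not impute no flare. Report the Kaplan-Meier cumulative proportion at Weeks 28 and 52, censoring at the last assessment of flare status. This assumes that censoring is unrelated to flare risk; a sensitivity analysis counting losses as events would show how much depends on that.

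The cost is a few sentences in the SAP and no new data. Section 5.4.1.3.3 already plans Kaplan-Meier curves for the same composite.

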Approximately 51 participants are planned to be enrolled into the study. The assumptions for the sample size and power calculation were based on the data from the Actemra Phase 3 GCA study. The GC-free remission rates at Week 28 are assumed to be 40% for placebo and 80% for guselkumab treatment arm. Based on these assumptions, 51 participants are planned to be randomized in a 2:1 ratio to either the guselkumab group or the placebo group. These sample sizes provide the study with 82% power to detect a difference in the primary endpoint between the 2 treatment groups.

For purposes of analysis, the following populations are defined:

- Enrolled: All participants who signed the informed consent form.
- Full Analyses Set: All participants who were randomized in the study and received at least one administration of study intervention.
- Safety Analysis Set: All participants who received at least one dose of study intervention.
- Immunogenicity Analysis Set: All participants who received at least 1 administration of guselkumab and have at least one sample obtained after their first dose of guselkumab.

- PK Analysis Set: All participants who received at least 1 administration of guselkumab and have at least one valid blood sample drawn for PK analysis.
- PD Analysis Set: All participants who received at least 1 administration of study intervention and have at least one post-dose sample collection.

Data primarily will be summarized using descriptive statistics. Continuous variables will be summarized using the number of observations, mean, standard deviation, median, interquartile range, minimum and maximum, as appropriate. Categorical values will be summarized using the number of observations and percentages as appropriate. Median time will be reported for time to event variables. In addition, graphical data displays (eg, line plots) and participant listings may also be used to summarize/present the data.

For continuous endpoints, Mixed-Effect Model Repeated Measure model and Analysis of Covariance will be used for analysis. For binary endpoints, a Cochran-Mantel-Haenszel test stratified by new-onset and relapsing GCA, and the baseline prednisone dose (≤ 30 mg/day or > 30 mg/day) will be used to analyze data. For time to first event data, Kaplan-Meier curves and Cox proportional hazards regression will be used to analyze the data. In addition, treatment differences and their associated 90% confidence intervals will be presented.

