To evaluate the PK and immunogenicity of guselkumab, in combination with a 26-week GC taper regimen, in adult participants with new-onset or relapsing GCA.	
Mean (standard deviation [SD]) serum concentrations of guselkumab through Week 52 in participants receiving active study intervention.
 
Number/proportion of participants with antibodies to guselkumab in participants receiving active study intervention.

Exploratory	
To explore the longer-term efficacy of guselkumab compared to placebo, in combination with a 26-week GC taper regimen, in adult participants with new-onset or relapsing GCA.	Proportion of participants in sustained remission through Week 52
To evaluate the changes in immune-markers to guselkumab compared to placebo, in combination with a 26-week GC taper regimen, in adult participants with new-onset or relapsing GCA.	
Change from baseline in CRP through Week 52
 
Change from baseline in ESR through Week 52

To explore the changes in pharmacodynamic (PD) markers and arterial vessel wall inflammation following administration of guselkumab in adult participants with new-onset or relapsing GCA.	
Assessment of IL-23 pathway related and disease related biomarkers in serum, whole blood, and peripheral blood mononuclear cell (PBMC) through Week 52.
 
Large-Vessel Imaging (fluorodeoxyglucose positron emission tomography/computed tomography [FDG-PET/CT]) changes from baseline at Week 52 (or flare)

Objectives	Endpoints
To explore changes in participant reported Clinical Outcome Assessments, pain and fatigue, and physician reported outcomes and digital health parameters following administration of guselkumab in adult participants with new-onset or relapsing GCA.	
Change from baseline on electronic patient-reported outcome (ePRO): Patient's Global Assessment of Disease Activity (PGA), Pain Assessment, Functional Assessment of Chronic Illness Therapy (FACIT)-Fatigue and short form-36 (SF-36) by visit through Week 52
 
Change from baseline on clinician reported outcome: Physician's Global Assessment of Disease Activity (PhGA) by visit through Week 52
 
Change from baseline in Actigraphy Watch collected continuous data on physical activity, mobility, and sleep by visit through Week 52

Exploratory Objectives for the Long-Term Extension (LTE) period	

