9.4.1. General Considerations

Data primarily will be summarized using descriptive statistics. Continuous variables will be summarized using the number of observations, mean, SD, median, interquartile range, minimum and maximum, as appropriate. Categorical values will be summarized using the number of observations and percentages as appropriate. Median time will be reported for time to event variables. In addition, graphical data displays (eg, line plots) and participant listings may also be used to summarize/present the data.

For continuous endpoints, Mixed-Effect Model Repeated Measure model and Analysis of Covariance will be used for analysis. For binary endpoints, Cochran-Mantel-Haenszel test stratified by new-onset and relapsing GCA, and the baseline prednisone dose (≤ 30 mg/day or > 30 mg/day) will be used to analyze data. For time to first event data, Kaplan-Meier curves and Cox proportional hazards regression will be used to analyze the data. In addition, treatment differences and their associated 90% confidence intervals will be presented.

In general, all statistical tests will be performed at a 2-sided significance level of $\alpha = 0.10$. No multiplicity adjustment will be made for the secondary endpoints being tested and nominal p values will be reported.

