9.4.4. Tertiary/Exploratory Endpoints

Other Efficacy Endpoints

- Proportion of participants in sustained remission through Week 52.

Sustained remission through Week 52 is defined as: No signs and symptoms of GCA through Week 52, and completion of the protocol defined GC taper, and not having required GC rescue therapy at any time by Week 52.

- Change from baseline in CRP through Week 52
- Change from baseline in ESR through Week 52

Clinical Outcome Assessments

- Change from baseline in PGA by visit through Week 52
- Change from baseline in Pain Assessment by visit through Week 52
- Change from baseline in SF-36 individual domains by visit through Week 52
- Change from baseline in FACIT-fatigue score by visit through Week 52
- Change from baseline in PhGA by visit through Week 52.

Further details of tertiary/exploratory endpoints analyses and analyses for efficacy during the LTE will be provided in the SAP.

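### ESR and CRP change from baseline: the objective is a comparison with placebo, but the SAP plans only group descriptive statistics (minor, exploratory)

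*SAP*

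**What the plan says.** **Protocol.** Section 9.4.1 states that for continuous endpoints "Mixed-Effect Model Repeated Measure model and Analysis of Covariance will be used for analysis". It and the synopsis add that "treatment differences and their associated 90% confidence intervals will be presented". Neither sentence is restricted to particular endpoints. Section 9.4.1 also opens with "Data primarily will be summarized using descriptive statistics". The introduction to Section 9.4 describes what follows as a summary for the most important endpoints, primary and key secondary among them. Section 9.4.4 adds: "Further details of tertiary/exploratory endpoints analyses and analyses for efficacy during the LTE will be provided in the SAP".

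**Objective.** In Protocol Section 3 the exploratory objective for the two inflammatory markers is "To evaluate the changes in immune-markers to guselkumab compared to placebo"; SAP 1.1 repeats it. The SAP 5.5 objective, which covers all main-study exploratory endpoints, is also comparative, though garbled: "To evaluate the efficacy of guselkumab with a compared to placebo".

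**SAP.** Section 5.5 lists "Change from baseline in CRP through Week 28 and from Week 28 through Week 52 by visit" and the same endpoint for ESR. Section 5.5.1.9 sets the rules for continuous endpoints at Weeks 28 and 52. After intercurrent events (ICEs) 1-3 a zero change is assigned, after ICE 4 observed data are used, and missing data are not imputed. The analysis is then "Simple descriptive statistics, such as n, mean, SD, median, IQ range, minimum and maximum for these continuous variables".

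**The concern.** An objective that asks how marker change differs from placebo is answered by two columns of summaries. No between-group difference, interval or test is planned for ESR or CRP change, and the models that the protocol names for continuous data are used for no endpoint in the SAP. The one continuous endpoint with a formal comparison, cumulative GC dose (SAP 5.4.1.3.2), uses a van Elteren test.

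From n, mean and SD a reader could build only an unadjusted contrast of change scores. With 34 versus 17 participants that contrast is less precise than one adjusted for baseline. What is at stake is the usefulness of an exploratory result; the primary endpoint and the secondary endpoints are not touched.

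**Working it through.** **1. Passages side by side**

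| Item | Protocol | SAP |
|---|---|---|
| ESR/CRP objective | Comparative (Section 3) | Comparative (1.1 and 5.5) |
| PRO and PhGA objective | Changes after guselkumab, no comparator named (Section 3) | Same in 1.1; comparative only through 5.5 |
| Method for continuous endpoints | MMRM and ANCOVA, difference and 90% CI (9.4.1, synopsis) | Group descriptives (5.5.1.9) |
| MMRM or ANCOVA used | Named generally | For no endpoint |
| Binary marker endpoints | Secondary endpoints combining remission with normalization | Secondary endpoints 2-4: CMH, difference and 90% CI at Week 28 (5.4.1.3.1); exploratory normalization endpoints follow the same approach (5.5.1.9) |

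The text therefore supports the mismatch most clearly for ESR and CRP change.

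**2. The plan's own figure**

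The documents give no design figure for any continuous exploratory endpoint. The only design calculation is the primary-endpoint power, and it reproduces. Pooled p = (17×0.40 + 34×0.80)/51 = 0.667; null SE = √(0.667×0.333×(1/17+1/34)) = 0.140; alternative SE = √(0.24/17+0.16/34) = 0.137; continuity correction = 0.5×(1/17+1/34) = 0.044. Then (0.40 − 0.044 − 1.645×0.140)/0.137 ≈ 0.915, so power is 82.0% against the stated 82%. The present point does not depend on it.

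**3. Illustrative precision, no ICEs**

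Inputs from the documents: n = 34 and 17, 90% CI. Assumed: baseline/follow-up correlation r = 0.3, 0.5 or 0.7, with the same SD at both times. The SE factor is √(1/34+1/17) = 0.297.

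- Unadjusted change score: half-width = t(0.95; 49 df) × 0.297 × √(2(1−r)) = 0.498 × √(2(1−r)) SD.
- ANCOVA with arm, baseline and two strata: half-width = t(0.95; 46 df) × 0.297 × √(1−r²) = 0.499 × √(1−r²) SD.

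| r | Unadjusted | ANCOVA | Narrower by |
|---|---|---|---|
| 0.3 | 0.589 | 0.476 | 19.3% |
| 0.5 | 0.498 | 0.432 | 13.3% |
| 0.7 | 0.386 | 0.356 | 7.7% |

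**4. With the zero-change rule kept**

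This was simulated with 20,000 trials per cell, bivariate normal data, change set to 0 for ICE 1-3 participants, and strata balanced by arm and not prognostic. Entries are mean half-widths in SD units, unadjusted versus ANCOVA.

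| ICE 1-3 rate, guselkumab/placebo (assumed) | r = 0.3 | r = 0.5 | r = 0.7 |
|---|---|---|---|
| 0% / 0% | 0.587 vs 0.479 (18.4%) | 0.495 vs 0.434 (12.4%) | 0.384 vs 0.359 (6.7%) |
| 10% / 30% | 0.536 vs 0.456 (14.9%) | 0.453 vs 0.407 (10.0%) | 0.350 vs 0.332 (5.2%) |
| 20% / 60% | 0.477 vs 0.422 (11.5%) | 0.404 vs 0.373 (7.6%) | 0.313 vs 0.300 (4.0%) |

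The 20%/60% pair treats every non-remitter under the design rates (80% and 40% remission) as an ICE. This is an upper case, because non-remission also includes stable active disease, taper non-adherence and missing data.

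**5. Chance baseline imbalance**

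A one-SE baseline difference (0.297 SD) moves the unadjusted contrast by (1−r) × 0.297 = 0.21, 0.15 or 0.09 SD. The unadjusted interval already contains this variation. It is the gain of steps 3 and 4 seen another way and must not be added to it.

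**The case against.** The strongest case against is that the SAP is entitled to do this. Protocol 9.4 presents itself as a summary for the most important endpoints, 9.4.1 puts descriptive statistics first, and 9.4.4 hands exploratory detail to the SAP. SAP Table 2 gives descriptive statistics as the summary measure even for secondary endpoints 5 and 7, so describing lower-ranked endpoints is a consistent choice. The SAP 5.1 statement that the two groups will be compared can be read as naming the pair of groups, without promising a test for every endpoint. All of this stands. A reader might infer that the SAP breaks a protocol commitment; the documents do not support that.

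Two other stronger readings also fail:

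- **That every continuous exploratory endpoint was promised a comparison.** For PGA, pain, SF-36, FACIT-Fatigue and PhGA, the specific objective in both documents names no comparator. Only the general SAP 5.5 sentence is comparative.
- **That the markers are never compared.** Secondary endpoints 2-4 compare remission with normalization, and the exploratory normalization endpoints follow that approach. The CMH test and 90% CI are explicit only at Week 28, so coverage at later visits is arguable. These are binary outcomes and do not estimate the size of marker change.

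The model also has a real weakness. At 20%/60% ICE rates about 0.60×17 ≈ 10 placebo values are exactly zero. The slope of change on baseline is then −(1−r)×0.8 for guselkumab and −(1−r)×0.4 for placebo, so a common-slope ANCOVA is only approximate. CRP may also be skewed.

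**Conclusion.** A minor, inexpensive improvement, confined to exploratory endpoints. For ESR and CRP change, the documents state a comparative objective and a general method for continuous data, and the SAP supplies neither a difference nor an interval. The protocol's own qualifications make this a mismatch to reconcile.

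The main benefit is an estimate with an interval where none is planned. The added precision, about 8% to 19% with no ICEs and about 4% to 15% under the zero-change rule, rests on assumed correlations, ICE rates and normality. The documents give none of these, so the figures are illustrative.

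A reader might also infer that the zero-change rule is faulty, because zero is not an unfavourable value for someone whose marker is already normal at baseline. The documents do not support calling it a defect. The rule is a legitimate composite choice in line with the primary estimand, and the size of any distortion cannot be derived from them. The rule should stay.

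**What to change.** In SAP 5.5.1.9, keep the descriptive tables and the ICE rules. For change from baseline in ESR and CRP at Weeks 28 and 52, add an ANCOVA (or an MMRM, since both markers are measured repeatedly) adjusting for the baseline value, baseline disease status and baseline GC dose stratum. Report the guselkumab-minus-placebo difference with a nominal 90% CI. Support it with a van Elteren test stratified by the same two factors, as already planned for cumulative GC dose, because assigned zeros and possible skewness make the model approximate.

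The same output may be added for the PRO and PhGA changes, but the case there is weaker, since only the SAP 5.5 objective is comparative.

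The cost is SAP wording and one model per endpoint, with no new data and no change to primary or secondary analyses. ESR and CRP at two timepoints give 2×2 = 4 nominal intervals without multiplicity control. Extending to PGA, pain, eight SF-36 domains, two SF-36 summary scores, FACIT-Fatigue and PhGA makes 16 variables and 32 intervals, of which about 32×0.10 ≈ 3 would exclude zero if there were no effect anywhere. That is a reason to keep the addition to ESR and CRP unless the wider set is wanted.
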